### **Subject data protection**

AstraZeneca will not provide individual genotype results to patients, any insurance company, any employer, their family members, general physician or any other third party, unless required to do so by law.

Extra precautions are taken to preserve confidentiality and prevent genetic data being linked to the identity of the patient. In exceptional circumstances, however, certain individuals might see both the genetic data and the personal identifiers of a patient. For example, in the case of a medical emergency, an AstraZeneca Physician or an investigator might know a patient's identity and also have access to his or her genetic data. Also Regulatory authorities may require access to the relevant files, though the patient's medical information and the genetic files would remain physically separate.

### **Data management**

Any genotype data generated in this study will be stored within the relevant tracking system at AstraZeneca and/or third party contracted to work with AstraZeneca to analyse the samples.

The results from this genetic research may be reported in the CSR for the main study, or in a separate report as appropriate.

Some or all of the clinical datasets from the main study may be merged with the genetic data in a suitable secure environment separate from the clinical database.

### **Statistical Methods and Determination of Sample Size**

The number of patients that will agree to participate in the genetic research is unknown. It is therefore not possible to establish whether sufficient data will be collected to allow a formal statistical evaluation or whether only descriptive statistics will be generated. A statistical analysis plan will be prepared where appropriate.

## **Appendix D Actions Required in Cases of Increases in Liver Biochemistry and Evaluation of Hy's Law**

### **Introduction**

This Appendix describes the process to be followed in order to identify and appropriately report cases of Hy's Law. It is not intended to be a comprehensive guide to the management of elevated liver biochemistries.

During the course of the study the Investigator will remain vigilant for increases in liver biochemistry. The investigator is responsible for determining whether a patient meets potential Hy's Law (PHL) criteria at any point during the study.

The Investigator participates, together with AstraZeneca clinical project representatives, in review and assessment of cases meeting PHL criteria to agree whether Hy's Law (HL) criteria are met. HL criteria are met if there is no alternative explanation for the elevations in liver biochemistry other than Drug-Induced Liver Injury (DILI) caused by the IP.

The Investigator is responsible for recording data pertaining to PHL/HL cases and for reporting AEs and SAEs according to the outcome of the review and assessment in line with standard safety reporting processes.

### **Definitions**

#### **Potential Hy's Law (PHL)**

Aspartate Aminotransferase (AST) or alanine aminotransferase (ALT)  $\geq 3 \times \text{ULN}$  **together with** total bilirubin  $\geq 2 \times \text{ULN}$  at any point during the study following the start of study drug irrespective of an increase in alkaline phosphatase (ALP).

#### **Hy's Law (HL)**

AST or ALT  $\geq 3 \times \text{ULN}$  **together with** total bilirubin  $\geq 2 \times \text{ULN}$ , where no other reason, other than the IP, can be found to explain the combination of increases, eg, elevated ALP indicating cholestasis, viral hepatitis, another drug.

For PHL and HL the elevation in transaminases must precede or be coincident with (ie, on the same day) the elevation in total bilirubin, but there is no specified timeframe within which the elevations in transaminases and total bilirubin must occur.

### **Identification of Potential Hy's Law Cases**

In order to identify cases of PHL it is important to perform a comprehensive review of laboratory data for any patient who meets any of the following identification criteria in isolation or in combination:

- ALT  $\geq 3 \times \text{ULN}$
- AST  $\geq 3 \times \text{ULN}$

- Total bilirubin  $\geq 2 \times \text{ULN}$

The Investigator will without delay review each new laboratory report and if the identification criteria are met will:

- Notify the AstraZeneca representative
- Determine whether the patient meets PHL criteria (see [Definitions](#) within this Appendix for definition) by reviewing laboratory reports from all previous visits
- Promptly enter the laboratory data into the laboratory CRF

### **Follow-up**

#### **Potential Hy's Law Criteria not met**

If the patient does not meet PHL criteria the Investigator will:

- Inform the AstraZeneca representative that the patient has not met PHL criteria.
- Perform follow-up on subsequent laboratory results according to the guidance provided in the Clinical Study Protocol.

#### **Potential Hy's Law Criteria met**

If the patient does meet PHL criteria the Investigator will:

- Determine whether PHL criteria were met at any study visit prior to starting study treatment (See [Actions Required When Potential Hy's Law Criteria are Met Before and After Starting Study Treatment](#))
- Notify the AstraZeneca representative who will then inform the central Study Team

The Study Physician contacts the Investigator, to provide guidance, discuss and agree an approach for the study patients' follow-up and the continuous review of data. Subsequent to this contact the Investigator will:

- Monitor the patient until liver biochemistry parameters and appropriate clinical symptoms and signs return to normal or baseline levels, or as long as medically indicated
- Investigate the aetiology of the event and perform diagnostic investigations as discussed with the Study Physician.
- Complete the three Liver CRF Modules as information becomes available
- If at any time (in consultation with the Study Physician) the PHL case meets serious criteria, report it as an SAE using standard reporting procedures

## Review and Assessment of Potential Hy's Law Cases

The instructions in this Section should be followed for all cases where PHL criteria are met.

No later than 3 weeks after the biochemistry abnormality was initially detected, the Study Physician contacts the Investigator in order to review available data and agree on whether there is an alternative explanation for meeting PHL criteria other than DILI caused by the IMP. The AstraZeneca Study Physician and Global Safety Physician will also be involved in this review together with other subject matter experts as appropriate.

According to the outcome of the review and assessment, the Investigator will follow the instructions below.

If there is an agreed alternative explanation for the ALT or AST and total bilirubin (TBL) elevations, a determination of whether the alternative explanation is an AE will be made and subsequently whether the AE meets the criteria for a SAE:

- If the alternative explanation is **not** an AE, record the alternative explanation on the appropriate CRF
- If the alternative explanation is an AE/SAE, record the AE /SAE in the CRF accordingly and follow the AZ standard processes

If it is agreed that there is **no** explanation that would explain the ALT or AST and TBL elevations other than the IMP:

- Report an SAE (report term 'Hy's Law') according to AstraZeneca standard processes.
  - The 'Medically Important' serious criterion should be used if no other serious criteria apply
  - As there is no alternative explanation for the HL case, a causality assessment of 'related' should be assigned.

If, there is an unavoidable delay, of over 3 weeks, in obtaining the information necessary to assess whether or not the case meets the criteria for HL, then it is assumed that there is no alternative explanation until such time as an informed decision can be made:

- Report an SAE (report term 'Potential Hy's Law') applying serious criteria and causality assessment as per above
- Continue follow-up and review according to agreed plan. Once the necessary supplementary information is obtained, repeat the review and assessment to determine whether HL criteria are met. Update the SAE report according to the outcome of the review

## **Actions Required When Potential Hy's Law Criteria are Met Before and After Starting Study Treatment**

This section is applicable to patients with liver metastases who meet PHL criteria on study treatment having previously met PHL criteria at a study visit prior to starting study treatment.

At the first on study treatment occurrence of PHL criteria being met the Investigator will:

- Determine if there has been a significant change in the patients' condition# compared with the last visit where PHL criteria were met#
  - If there is no significant change no action is required
  - If there is a significant change notify the AstraZeneca representative, who will inform the central Study Team, then follow the subsequent process described in [Potential Hy's Law Criteria met](#) of this Appendix

# A 'significant' change in the patient's condition refers to a clinically relevant change in any of the individual liver biochemistry parameters (ALT, AST or total bilirubin) in isolation or in combination, or a clinically relevant change in associated symptoms. The determination of whether there has been a significant change will be at the discretion of the Investigator, this may be in consultation with the Study Physician if there is any uncertainty.

## **Actions Required for Repeat Episodes of Potential Hy's Law**

This section is applicable when a patient meets PHL criteria on study treatment and has already met PHL criteria at a previous on study treatment visit.

The requirement to conduct follow-up, review and assessment of a repeat occurrence(s) of PHL is based on the nature of the alternative cause identified for the previous occurrence.

The Investigator should determine the cause for the previous occurrence of PHL criteria being met and answer the following question:

- Was the alternative cause for the previous occurrence of PHL criteria being met found to be the disease under study e.g. chronic or progressing malignant disease, severe infection or liver disease, or did the patient meet PHL criteria prior to starting study treatment and at their first on study treatment visit as described in Actions Required When Potential Hy's Law Criteria are Met Before and After Starting Study Treatment?

If No: follow the process described in [Potential Hy's Law Criteria met](#) of this Appendix

If Yes:

Determine if there has been a significant change in the patient's condition# compared with when PHL criteria were previously met

- If there is no significant change no action is required

- If there is a significant change follow the process described in Section 4.2 of this Appendix

# A 'significant' change in the patient's condition refers to a clinically relevant change in any of the individual liver biochemistry parameters (ALT, AST or total bilirubin) in isolation or in combination, or a clinically relevant change in associated symptoms. The determination of whether there has been a significant change will be at the discretion of the Investigator; this may be in consultation with the Study Physician if there is any uncertainty.

## **Appendix E Acceptable Birth control Methods**

### **Osimertinib is regarded as a compound with medium/high foetal risk**

Patients of childbearing potential and their partners, who are sexually active, must agree to the use of 2 highly effective forms of contraception throughout their participation in the study and for 3 months (females) and 6 months (males) after last dose of study drug.

#### **Acceptable non-hormonal birth control methods include:**

- True sexual abstinence. When this is in line with the preferred and usual lifestyle of the patient. [*Periodic abstinence (eg, calendar, ovulation, symptothermal, post-ovulation methods) and withdrawal are not acceptable methods of contraception*]. Abstinence must be for the total duration of the study and until 3 months (females) and 6 months (males) after discontinuation of study treatment.
- Vasectomised sexual partner plus male condom. With participant assurance that partner received post-vasectomy confirmation of azoospermia.
- Tubal occlusion plus male condom with spermicide
- Intrauterine device (IUD) plus male condom + spermicide. Provided coils are copper-banded.

#### **Acceptable hormonal methods:**

- IUS Levonorgestrel Intra Uterine System (Mirena) + male condom with spermicide
- Medroxyprogesterone injections (Depo-provera) + male condom with spermicide.

## **Appendix F Eastern Cooperative Oncology Group (ECOG) Performance Status**

| Patient ability  | Score |
|---|--------------|
| Fully active, able to carry on all pre-disease performance without restriction  | 0            |
| Restricted in physically strenuous activity but ambulatory and able to carry out work of a light or sedentary nature, eg, light house work, office work | 1            |
| Ambulatory and capable of all self-care, but unable to work. Up and about more than 50% of waking hours   | 2            |
| Capable of only limited self-care, confined to bed or chair more than 50% of waking hours   | 3            |
| Completely disabled, unable to carry out any self-care and confined totally to bed or chair   | 4            |

## Appendix G Guidance Regarding Potential Interactions with Concomitant Medications

The use of any natural/herbal products or other “folk remedies” should be discouraged, but use of these products, as well as use of all vitamins, nutritional supplements, and all other concomitant medications must be recorded in the eCRF.

### Drugs Inducing CYP3A4 Metabolism that AstraZeneca Strongly Recommend are Not Combined with Osimertinib

Osimertinib is metabolised by CYP3A4 and CYP3A5 enzymes.

A drug-drug interaction study of osimertinib evaluated in patients showed that there is potential for osimertinib being a victim when co-administered with strong inducers of CYP3A4 (osimertinib concentrations are decreased when co-dosed with rifampicin).

The following potent inducers of CYP3A4 must not be used during this study for any patient receiving osimertinib (Table 7).

**Table 7 Drugs inducing CYP3A4**

| Contraindicated drugs  | Withdrawal period prior to osimertinib start |
|--|--|
| Carbamazepine, phenobarbital, phenytoin, rifampicin, rifabutin, rifapentin
St John’s Wort | 3 weeks                                      |
| Phenobarbitone   | 5 weeks                                      |

This list is not intended to be exhaustive, and a similar restriction will apply to other agents that are known to strongly modulate CYP3A4 activity. Appropriate medical judgment is required. Please contact AstraZeneca with any queries you have on this issue.

### Medicines Whose Exposures May be Affected by Osimertinib that AstraZeneca Considers May be Allowed with Caution

Osimertinib may increase the concentration of sensitive breast cancer resistance protein (BCRP) substrates (concentration of the sensitive BCRP substrate, rosuvastatin, is increased). This list is not intended to be exhaustive, and a similar restriction will apply to other agents that are known to be modulated BCRP activity. Appropriate medical judgment is required. Please contact AstraZeneca with any queries you have on this issue.

**Table 8 Exposure, pharmacological action and toxicity may be increased by osimertinib**

| Warning of possible interaction | Advice   |
|---------------------------------|--|
| Rosuvastatin
Sulfasalazine   | Drugs are permitted but caution should be exercised and patients monitored closely for |

**Table 8 Exposure, pharmacological action and toxicity may be increased by osimertinib**

| Warning of possible interaction   | Advice   |
|--|---|
| Doxorubicin
Daunorubicin
Topotecan | possible drug interactions. Please refer to full prescribing information for all drugs prior to co-administration with osimertinib. |

### **Drugs that May Prolong QT Interval**

The drugs listed in this section are taken from information provided by The Arizona Center for Education and Research on Therapeutics and The Critical Path Institute, Tucson, Arizona and Rockville, Maryland. Ref: <http://www.arizonacert.org/medical-pros/drug-lists/drug-lists.htm>.

### **Drugs Known to Prolong QT Interval**

The following drugs are known to prolong QT interval or induce Torsades de Pointes and should not be combined with osimertinib. Recommended withdrawal periods following cessation of treatment with these agents are provided in Table 9.

**Table 9 Drugs prolonging QT interval**

| Contraindicated drug   | Withdrawal period prior to osimertinib start |
|---|---|
| Clarithromycin, droperidol, erythromycin, procainamide  | 2 days  |
| Cisapride, disopyramide, dofetilide, domperidone, ibutilide, quinidine, sotalol, sparfloxacin, thioridazine | 7 days  |
| Bepidil, chlorpromazine, halofantrine, haloperidol, mesoridazine  | 14 days   |
| Levomethadyl, methadone, pimozone   | 4 weeks   |
| Arsenic trioxide  | 6 weeks*  |
| Pentamidine   | 8 weeks   |
| Amiodarone, chloroquine   | 1 year  |

\* Estimated value as pharmacokinetics of arsenic trioxide has not been studied

### **Drugs that may possibly prolong QT interval**

The use of the following drugs is permitted (notwithstanding other exclusions and restrictions) provided the patient has been stable on therapy for the periods indicated ([Table 10](#)).

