### 3.2 Exclusion criteria

Patients should not enter the study if any of the following exclusion criteria are fulfilled:

1. Involvement in the planning and/or conduct of the study (applies to both AstraZeneca staff and/or staff at the study site)
2. Participation in another clinical study with an investigational product during the last 14 days (or a longer period, depending on the defined characteristics of the agents used).
3. Treatment with any of the following:
  - A 1st or 2nd generation EGFR-TKI (eg, afatinib, erlotinib or gefitinib) within 8 days or approximately 5 half-lives, whichever is the longer, of the first dose of study treatment (if sufficient wash-out time has not occurred due to schedule or PK properties, an alternative appropriate wash-out time based on known duration and time to reversibility of drug related AEs could be agreed upon by AstraZeneca and the Investigator).
  - Osimertinib in the present study (ie, dosing with osimertinib previously initiated in this study) or has previously received a 3rd generation EGFR-TKI (eg, CO-1686). Patients who were enrolled, screened but not dosed (ie, withdrew from the study prior to dosing) may be re-enrolled and rescreened if in the opinion of the Investigator, the reason(s) for earlier withdrawal no longer applies.
  - Any cytotoxic chemotherapy, investigational agents or other anticancer drugs from a previous treatment regimen or clinical study within 14 days of the first dose of study treatment.
  - Major surgery (excluding placement of vascular access) within 4 weeks of the first dose of study treatment.
  - Radiotherapy with a limited field of radiation for palliation within 1 week of the first dose of study treatment, with the exception of patients receiving radiation to more than 30% of the bone marrow, or with a wide field of radiation which must be completed within 4 weeks of the first dose of study treatment.

- Patients currently receiving (or unable to stop use at least 3 weeks prior to receiving the first dose of osimertinib) medications or herbal supplements known to be potent inducers of CYP3A4 or inducers/inhibitors of P-gp, as described in [Appendix G](#).
4. Any unresolved toxicities from prior therapy greater than Common Terminology Criteria for Adverse Events (CTCAE) Grade 1 at the time of starting study treatment; with the exception of alopecia and Grade 2 prior platinum-therapy related neuropathy.

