- Follow-up assessments will only be performed for patients who permanently discontinue osimertinib treatment during the PK phase. On completion of the PK phase, patients may continue to take osimertinib tablets as a single agent until such time as the Investigator believes they are no longer deriving clinical benefit or they stop taking osimertinib for any other reason.
- Compliance with comedication and/or food/beverage restrictions related to CYP3A4 and P-gp activity must be maintained during Day -1 and Day 1.

Clinical Study Protocol  
Drug Substance Osimertinib (AZD9291)  
Study Code D5160C00036  
Version 1.0

C check; D = drug dispensed; ECG electrocardiogram; ECHO echocardiogram; ECOG Eastern Cooperative Oncology Group; HBV hepatitis B; HCV hepatitis C Virus; MUGA multiple gated acquisition scan; P provided; PK pharmacokinetics; R drug returned.

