### **8.3.3 PK analysis set**

The PK analysis set will include all patients who receive a fexofenadine and/or an osimertinib dose and have at least 1 quantifiable plasma concentration collected post-dose without important protocol deviations/violations or events thought to significantly affect the PK of the IP.

The pharmacokineticist will agree on the strategy for dealing with data affected by important protocol deviations or events before any formal statistical analysis is performed. Important protocol deviations or events include changes to the procedures that may impact the quality of the data or any circumstances that can alter the evaluation of the PK. Examples include, but may not be limited to, vomiting following oral dosing occurring within the timeframe of 2 times the median  $t_{max}$ , sample processing errors that lead to inaccurate bioanalytical results, incomplete dose administered or timing of the dose, incomplete PK profile collected and/or changes in concomitant medications affecting P-gp that may affect the PK results, and/or use of disallowed concomitant medication. In the case of an important protocol deviation or event, affected PK data collected will be excluded from the summaries and statistical analyses, but will still be reported in the study result listings. Important deviations will be listed and summarised in the CSR.

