**Table 10**                    **Drugs that may prolong QT interval**

| Drug  | Minimum treatment period on medication prior to osimertinib start |
|--|--|
| Alfuzosin, chloral hydrate, ciprofloxacin, dolasetron, foscarnet, galantamine, gemifloxacin, isridipine, ketoconazole, levofloxacin, mexiletine, nocardipine, octreotide, ofloxacin, ondansetron, quetiapine, ranolazine, telithromycin, tizanidine, vardenafil, venlafaxine, ziprasidone    | 2 days   |
| Amantadine, amitriptyline, amoxapine, clozapine, doxepin, felbamate, flecainide, fluconazole, fosphenytoin, gatifloxacin, granisetron, imipramine, indapamide, lithium, moexipril/HCTZ, moxifloxacin, risperidone, roxithromycin, sertraline, trimethoprim-sulfa, trimipramine, voriconazole | 7 days   |
| Azithromycin, citalopram, clomipramine, itraconazole, nortriptyline, paroxetine, solifenacin, tacrolimus   | 14 days  |
| Fluoxetine   | 5 weeks  |
| Protriptyline  | 6 weeks  |
| Tamoxifen  | 8 weeks  |

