**Table 11**                    **Drugs inducing P-gp**

| Contraindicated drugs   | Withdrawal period prior to fexofenadine start |
|--|--|
| Avasimibe, carbamazepine, efavirenz, genistein (found in food products), phenytoin, quercetin (found in food products), rifampicin, St John's Wort, tipranavir/ritonavir | 3 weeks  |

The following inhibitors of P-gp must not be used during this study for any patient in Part A of the study or should not be changed during the treatment period (Table 12).

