**Table 12 Drugs inhibiting P-gp**

| Contraindicated drugs   | Withdrawal period prior to fexofenadine start  |
|--|---|
| Alogliptin, amiodarone, , azithromycin, captopril, carvedilol, clarithromycin, clopidogrel, conivaptan, curcumin, cyclosporine, diltiazem, dronedarone, eliglustat, erythromycin, felodipine, fluvoxamine, indinavir, indinavir/ritonavir, itraconazole, ivacaftor, ketoconazole, lapatinib, lopinavir/ritonavir, mibefradil, milk thistle, nelfinavir, paroxetine, propafenone, quercetin (found in food products), quinidine, quinine, ranolazine, rifampicin, ritonavir, saquinavir/ritonavir, schisandra chinensis extract, simeprevir, St John’s Wort (single dose), suvorexant, telaprevir, ticagrelor, tipranavir/ritonavir, valsopodar (PSC 833), verapamil, vorapaxar | 3 weeks   |
| Allowed drugs   |   |
| Canagliflozin, cremophor RH40, ginkgo, mirabegron, nifedipine, nitrendipine, talinolol, telmisartan, tolvaptan, vandetanib, voclosporin  | Medication should not be changed (adjusted or discontinued) within 10 days of Day 1, Period 1 in Part A through collection of the last planned PK sample in Part A (Day 42, 72 hours) unless medically necessary. |

This list is not intended to be exhaustive, and a similar restriction will apply to other agents that are known to strongly modulate P-gp activity. Appropriate medical judgment is required. Please contact AstraZeneca with any queries you have on this issue.

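### Appendix G's Table 10 overrides the P-gp inhibitor ban for five drugs that Table 12 prohibits in the PK phase

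*Protocol*

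**What the plan says.** Two rules in Appendix G cover the same drugs.

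**Permission.** The text over Table 10 reads: "The use of the following drugs is permitted (notwithstanding other exclusions and restrictions) provided the patient has been stable on therapy". The two-day row includes "ketoconazole, levofloxacin, mexiletine, nocardipine, octreotide, ofloxacin, ondansetron, quetiapine, ranolazine"; the 14-day row is "Azithromycin, citalopram, clomipramine, itraconazole, nortriptyline, paroxetine, solifenacin, tacrolimus". Both periods are counted back from the start of osimertinib.

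**Prohibition.** The text over Table 12 reads: "The following inhibitors of P-gp must not be used during this study for any patient in Part A of the study". Its contraindicated row includes "indinavir/ritonavir, itraconazole, ivacaftor, ketoconazole, lapatinib", and also azithromycin, paroxetine and ranolazine, all with three weeks' withdrawal before fexofenadine. The paragraph that opens this part of Appendix G extends the bar to the last PK sample on Day 42. I take Part A to be the PK phase, as the heading there indicates.

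Elsewhere, exclusion criterion 3 (Section 3.2) bars drugs "known to be potent inducers of CYP3A4 or inducers/inhibitors of P-gp, as described in" Appendix G. Sections 3.8 and 7.7 ask patients to try to avoid P-gp modulators where feasible. A Table 1 footnote says: "Compliance with comedication and/or food/beverage restrictions related to CYP3A4 and P-gp activity must be maintained during Day -1 and Day 1". Section 8.3.3 lists among deviations that can remove PK data "changes in concomitant medications affecting P-gp that may affect the PK results, and/or use of disallowed concomitant medication".

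**The concern.** The word *notwithstanding* gives Table 10 precedence over other exclusions and restrictions. The drafter probably meant *subject to*, which has the opposite effect. As written, a patient stable on paroxetine is permitted by Table 10 and ineligible under Table 12, while Sections 3 and 3.4 allow a site no eligibility exceptions.

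Fexofenadine is the P-gp probe and each patient serves as their own control, so P-gp co-medication has to be the same, preferably absent, in all three profiles. Two things can go wrong:

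- **Imbalance (ketoconazole, ranolazine).** A drug started after the reference dose is in both test profiles but missing from all or the early part of the reference. The result looks like P-gp inhibition by osimertinib, and on Day 39 it could hide induction.
- **Dilution (azithromycin, itraconazole, paroxetine).** A drug present throughout may leave P-gp already inhibited, so an osimertinib effect shows less.

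**Working it through.** **1. Overlap.** Table 10 has 22 + 22 + 8 + 1 + 1 + 1 = 55 entries. Matching them by name gives:

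| Drug | Table 10: time on drug before osimertinib | Table 12: withdrawal before fexofenadine |
|---|---|---|
| Ketoconazole | 2 days | 3 weeks |
| Ranolazine | 2 days | 3 weeks |
| Azithromycin | 14 days | 3 weeks |
| Itraconazole | 14 days | 3 weeks |
| Paroxetine | 14 days | 3 weeks |

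No Table 10 drug appears by name in Table 11.

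**2. Timing.** The reference fexofenadine dose precedes osimertinib by 3 to 7 days (Section 7.2.1). The latest start that Table 10 allows is therefore:

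- two-day drugs: (3 to 7) − 2 = 1 to 5 days *after* the reference dose;
- 14-day drugs: 14 − (3 to 7) = 7 to 11 days *before* it.

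Reference sampling runs for 72 hours. A start on day 1 after the dose leaves the first 24 hours free of inhibitor; a start on day 5 misses the whole profile.

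**3. The plan's own precision figure.** Section 8.2 gives 18 evaluable patients, intra-subject CV 30%, ratio 1.00, and 90% probability of a CI within 0.70 to 1.43. On the log scale s = √ln(1 + 0.30²) = 0.2936. With SE = s√(2/18), the exact probability for one comparison is 0.946 on 34 df (three-treatment mixed model) or 0.936 on 17 df (paired). Both comparisons jointly give 0.903 by simulation, so the stated 90% is reproduced and is not in dispute.

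**4. Imbalance.** If k of 18 patients carry an inhibitor with fold-effect f in the test profile only, the ratio is multiplied by f^(k/18). The value 1.25 is the threshold in Appendix G; f = 2, f = 3 and every k are assumptions.

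| f | k = 1 | P(CI within limits) | k = 3 | P(CI within limits) |
|---|---|---|---|---|
| 1.25 | 1.012 | 0.945 | 1.038 | 0.930 |
| 2 | 1.039 | 0.929 | 1.12 | 0.781 |
| 3 | 1.063 | 0.902 | 1.20 | 0.541 |

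The unbiased probability on the same basis (34 df) is 0.946.

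**5. Dilution.** Assume as a worst case that one patient of 18 shows no osimertinib effect. A true ratio R then reads R^(17/18): 1.25 → 1.23, 1.50 → 1.47, 0.70 → 0.71.

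**6. If the patient's data are removed.** One of the 24 − 18 = 6 spare patients is used. With none spare, the 90% CI half-width t(0.95, 2(n−1)) × s × √(2/n) goes from 0.1655 (n = 18) to 0.1706 (n = 17), a factor of 1.031. At ratio 1.00 the interval moves from 0.848–1.180 to 0.843–1.186, still well inside 0.70–1.43.

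**7. Whether other text resolves the conflict.** Exclusion 3 points to Appendix G, where the conflict sits. Exclusion 7 concerns drugs known to prolong QT, whereas Table 10 lists those that only may. The Table 1 footnote names Day −1 and Day 1 and is attached to those Treatment Period 1 visits, so it does not reach a drug started later.

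**The case against.** The best defence is that a sensible reader would still apply the ban. Only Tables 11 and 12 describe P-gp drugs, so exclusion 3 leads there; they are the specific rule for fexofenadine; and Table 10 can be read as the QT rule alone, useful mainly in continued access. The parenthesis might lift only Section 7.7's restriction on drugs that may prolong QT. This is a plausible account of intent, but it requires reading down an express override, and Sections 3.8 and 7.7 ask for avoidance only where feasible.

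The second argument is stronger. Section 8.3.3 has two limbs, and the first, a change in P-gp co-medication, catches an inhibitor started between periods whether or not Table 10 permits it. Section 7.7 also asks for regular medication to be maintained, and co-medication is recorded at every visit. That stands as real mitigation of the imbalance. It works only after the patient has been dosed and sampled, and may cost an evaluable patient. For a stable 14-day drug there is no change to catch, and the second limb does not say whether a drug that Table 10 permits is disallowed.

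It is also fair that a stable inhibitor does not by itself bias a within-patient ratio, and that drugs started to treat adverse events remain allowed with or without the edit.

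**Conclusion.** The contradiction is real and affects an operative eligibility and co-medication rule that protects the primary comparison. It should be corrected, though it does not threaten the trial. With one affected patient of 18 the ratio shifts by 1.2% (1.25-fold) to 3.9% (assumed 2-fold), or an osimertinib effect is diluted by about 1% to 2% over the ratios considered. If the data are dropped, the interval widens by about 3% at most. Calling the bias small assumes one or two users with modest inhibition. Three users at 2-fold would raise the ratio by 12% and cut the probability in Section 8.2 from 0.946 to 0.781, before any exclusion under Section 8.3.3. The Protocol gives neither the inhibitors' effects nor the number of users expected. The sample size is unaffected.

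A lesser inconsistency sits in Table 9: clarithromycin and erythromycin (2 days) and quinidine (7 days) carry shorter withdrawal periods than the three weeks in Table 12. Both tables contraindicate them, so only the governing period needs stating. Amiodarone is unaffected because its one-year period in Table 9 is already the longer.

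**What to change.** Make two edits in Appendix G:

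1. In the sentence over Table 10, replace *notwithstanding* with *subject to*.
2. Add one sentence: in the PK phase, Tables 11 and 12 govern any drug that also appears in Table 9 or 10, from three weeks before the first fexofenadine dose through the final PK sample on Day 42, and a QT withdrawal period longer than three weeks still applies.

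Keep the exception for treating adverse events in Sections 3.8 and 7.7, with Section 8.3.3 handling the affected data. The overlap between permitted and prohibited drugs then falls from five to none. Sample size and analysis do not change. The cost is that a few patients taking these drugs may be deferred or not enrolled.
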